3.3.4.1 Discontinuation of trial treatment

An individual patient will discontinue trial treatment if:

- The patient wants to discontinue trial treatment or if parent(s)/legal guardian want(s) the patient to discontinue trial treatment. They will be asked to explain the reasons but have the right to refuse to answer.
- The patient has repeatedly shown to be non-compliant with important trial procedures and, in the opinion of both the investigator and sponsor representative, the safety of the patient cannot be guaranteed as he / she is not willing or able to adhere to the trial requirements in the future.

In the following cases discontinuation of trial medication is highly recommended. Only in special circumstances the investigator, upon thorough assessment of all available clinical data and taking into consideration the potential risks associated with administration of nintedanib, may decide not to withdraw the trial medication, even though one or more of the below mentioned criteria are fulfilled. In such a case, continuation of treatment with trial medication should be discussed with the patient/parent(s)/legal guardian, and the decision and reasoning documented in the source data.

- Major surgery, including any abdominal or intestinal surgery.
- Anti-coagulation. Patients who require full-dose therapeutic anticoagulation (e.g. vitamin K antagonists, heparin, hirudin, direct thrombin inhibitors, etc.), or high-dose antiplatelet therapy. Prophylactic low dose heparin or heparin flush as needed for maintenance of an indwelling intravenous device, as well as prophylactic use of antiplatelet therapy is allowed.
- Major thrombo-embolic events e.g. stroke, deep vein thrombosis, pulmonary embolism, myocardial infarction.
- Increased risk of bleeding e.g. haemorrhagic CNS event, gross / frank haemoptysis or haematuria, active GI-bleeding or GI-ulcers.

In case of a temporary reason, trial treatment should be restarted if medically justified, please see [Section 4.1.4](#)

In case, the laboratory results at Visit 2 do no longer satisfy the entry criteria, the Investigator has to decide whether it is justified that the patient remains on study drug. The justification for decision needs to be documented in the patient's medical records.

The trial medication has to be permanently discontinued in the following circumstances:

- The patient experiences signs of hepatic injury attributable to trial drug, as defined in [Section 5.2.7.1.4](#).

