4.2.1.2 Management of liver enzyme elevations

Nintedanib can be associated with increased liver enzymes. Concomitant use of other drugs known to cause liver enzyme elevations should be evaluated. For a detailed guidance on how to manage liver enzyme elevations, please refer to [Table 4.2.1.2: 1](#) for patients.

Table 4.2.1.2: 1 Recommendations for managing liver enzyme elevations

	AST or ALT increase to			Signs of hepatic injury*
	>1.5x to <3x ULN	≥3x to <5x ULN and no signs of hepatic injury	≥5x to <8x ULN and no signs of hepatic injury	
At Visit 2 for new patients (start of treatment)	Permanently discontinue trial medication or justify continuation ¹	Permanently discontinue trial medication	Permanently discontinue trial medication	Permanently discontinue trial medication
At any other Visit for new patients and At all visits for roll-over patients	Continue as planned ²	Reduce dose or interrupt trial medication ³	Interrupt trial medication	Interrupt trial medication (may subsequently need to be permanently discontinued ⁵)
		Close observation ⁴ After 2 weeks or any time later	Close observation ⁴ After 2 weeks or any time later	CLINICAL EVALUATION OF HEPATIC-INJURY
	<3x ULN	≥3x ULN	<3x ULN	≥3x ULN
	Reduced: return to initial dose. Interrupted: restart at reduced dose. Monitor every 2 weeks for at least 8 weeks	Permanently discontinue trial medication Close observation ⁴	Restart at reduced dose Monitor weekly for 4 weeks, then every 2 weeks for at least 8 weeks	Permanently discontinue trial medication. Close observation ⁴

Footnotes:

*Signs of hepatic injury are defined as

- ALT and/or AST ≥ 8 fold ULN
- ALT and/or AST ≥ 3 fold ULN and total bilirubin ≥ 2 fold ULN
- ALT and/or AST ≥ 3 fold ULN and unexplained INR >1.5
- ALT and/or AST ≥ 3 fold ULN and unexplained eosinophilia ($>5\%$)
- ALT and/or AST ≥ 3 fold ULN and appearance of fatigue, nausea, vomiting, right upper abdominal quadrant pain or tenderness, fever and/or rash

¹Investigator to confirm in writing that continuation is justified (e.g. intermittent fluctuation of transaminases).

²According to visit schedule. Consider additional control visits as adequate.

³To be decided by Investigator, based on individual risk assessment.

⁴Close observation: Re-test ALT and AST, alkaline phosphatase, total bilirubin, and eosinophils within 48 to 72 hours, then approximately 7 days, then approximately 2 weeks, preferably by using appropriate visit lab kit as instructed to site by the sponsor.

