Test results must be documented in the patient's pregnancy test diary card and will be transferred to the patient's records by site staff at the next site visit. In case of positive results, procedures defined in [Section 5.2.7.2.3](#) should be followed.

At 'a-Visits', safety blood, and urine samples will be collected and submitted to the central laboratory if needed for additional safety monitoring at the discretion of the Investigator (see cautionary notes under [Section 4.2.2.1](#) for additional safety monitoring). Safety laboratory parameters to be assessed at regular visits are listed in [Table 5.2.3:1](#) Safety laboratory parameters to be assessed at these additional visits are listed in [Table 5.2.3:2](#).

The samples may be collected at the office of a local doctor using preferably trial specific lab kits that will be sent to a central laboratory for analyses or may be analysed locally. These kits will be provided to patients at study visits as applicable. Around 2.5 mL will be taken at each a-Visit.

If laboratory values indicate abnormality, adequate and more frequent blood sampling may be performed at the discretion of the Investigator.

In case of liver function value elevations, close monitoring must be ensured by the Investigator. Refer to [Section 4.1.2](#) for monitoring elevations and [Section 3.3.4](#) for withdrawal criteria.

In case the criteria for hepatic injury are fulfilled, a number of additional measures will be performed (please see [Section 5.2.7.1](#) and the DILI Checklist provided in the eDC system). The amount of blood taken from the patient concerned will be increased due to these additional samplings.

The central laboratory will transfer the results of the analysis to the sponsor or delegate.

Table 5.2.3:1 Safety laboratory tests at scheduled site visits

The laboratory tests at regular site visits will include:

Functional lab group	Test name
Haematology	Haematocrit Haemoglobin Red blood cells (RBC) White blood cells (WBC) Platelet count Mean corpuscular volume (MCV)
Automatic WBC differential (relative and absolute)	Neutrophiles total Lymphocytes total Eosinophiles Basophiles

Functional lab group	Test name
	Monocytes Lymphocytes
Manual differential WBC (if automatic differential WBC is abnormal)	Polymorphonuclear neutrophils (segs), band neutrophils (stabs), eosinophils, basophils, monocytes, lymphocytes
Coagulation	Activated partial thromboplastin time (aPTT) Prothrombin Time (PT) INR

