5.2.7.1.4 Adverse events of special interest

The term adverse events of special interest (AESI) relates to any specific AE that has been identified at the project level as being of particular concern for prospective safety monitoring and safety assessment within this trial, e.g. the potential for AEs based on knowledge from other compounds in the same class. AESIs need to be reported to the sponsor’s Pharmacovigilance Department within the same timeframe that applies to SAEs, please see [Section 5.2.7.2.2](#).

The following are considered as AESIs:

- adverse events relating to gastrointestinal perforation
- bleeding
- hepatic injury.
- pathological findings identified on bone imaging
- stunted growth identified on dental imaging.

Hepatic injury

In this trial protocol, signs of hepatic injury are defined as:

- ALT and/or AST ≥ 8 fold ULN
- ALT and/or AST ≥ 3 fold ULN and total bilirubin ≥ 2 fold ULN*
- ALT and/or AST ≥ 3 fold ULN and unexplained INR $> 1.5^*$
- ALT and/or AST ≥ 3 fold ULN and unexplained eosinophilia ($>5\%$)*
- ALT and/or AST ≥ 3 fold ULN and appearance of fatigue, nausea, vomiting, right upper abdominal quadrant pain or tenderness, fever and/or rash

*in the same blood draw sample.

These lab findings constitute a hepatic injury alert and the patients showing these lab abnormalities need to be followed up according to the “DILI checklist” provided in the eDC system.

In case of clinical symptoms of hepatic injury (icterus, unexplained encephalopathy, unexplained coagulopathy, right upper quadrant abdominal pain, etc.) without lab results (ALT, AST, total bilirubin) available, the investigator should make sure these parameters are analysed, if necessary, in an unscheduled blood test. Should the results meet the criteria of hepatic injury alert, the procedures described in the DILI checklist should be followed.

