$$\text{Sum of all treatment interruption durations [days]}$$

Total dose [g] will be calculated as

$$\text{Sum of durations of exposure on } x \text{ g [days]} * 2 * x \text{ g,}$$

with x in 0.025, 0.05, 0.075, 0.1, 0.15 and summarised as continuous variable.

Dose intensity [%] will be calculated as the amount of drug actually administered divided by the amount of drug that would have been administered, i.e. dose xx mg bid (depending on the body weight) during the planned treatment period (or until study discontinuation), multiplied by 100%. Dose intensity will be summarised as continuous variable and in categories [%]:

- ≤ 30
- > 30 to 50
- > 50 to 90
- > 90 to < 100
- ≥ 100

Exposure-related time-to-event analyses will be performed for the following items:

- Time to first dose reduction (not due to weight-based adjustment) [days]^[1]
- Time to first treatment interruption [days]
- Time to premature treatment discontinuation [days]

^[1] Will only be calculated for patients who started the trial on full dose according to their weight bin at baseline.

Time-to-event [days] for exposure-related analyses is derived based on first trial drug intake as

$$\text{Date of event/censoring} - \text{Date of first trial drug intake [days]} + 1 \text{ day}$$

For the above mentioned time-to-event analyses patients with no such event occurred during the trial will be censored according to the mechanism for censoring as described in [Table 5.4.3: 1](#).

Table 5.4.3: 1 Censoring rules for exposure-related time-to-event analyses

Rule #	Situation	Outcome (Event/Censored)	Date of event/censoring
1	Patient had a documented event and the date of the event is known	Event	Earliest date of event
2	Patient had a documented event and the date of the event is unknown	Event	Imputed date of event (as defined in Section 6.6.3.3)
3	Patient had no documented event and already terminated trial drug (last intake on End of treatment eCRF page available)	Censored	Date of last trial drug intake
4	Patient neither had a documented event nor terminated trial drug permanently (only applicable for potential interim analyses)	Censored	Date of interim data snapshot

These times will also be summarised in categories [weeks] as defined for duration of exposure [weeks] above.

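### When signs of hepatic injury are judged drug-related but the diagnosis is unconfirmed or pending, Section 3.3.4.1 requires a permanent stop while Table 4.2.1.2:1 only interrupts

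*Protocol*

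**What the plan says.** **Protocol Section 3.3.4.1** opens its mandatory list with "The trial medication has to be permanently discontinued in the following circumstances". The first entry reads "The patient experiences signs of hepatic injury attributable to trial drug, as defined in" Section 5.2.7.1.4. The trigger is signs plus attribution to the drug. Neither a confirmed diagnosis nor contact with the sponsor is a condition.

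**Protocol Section 5.2.7.1.4** defines the signs as five threshold criteria, for example ALT and/or AST at least 8-fold ULN, or at least 3-fold ULN with total bilirubin at least 2-fold ULN. It treats the laboratory findings as something to be worked up: "These lab findings constitute a hepatic injury alert and the patients showing these lab abnormalities need to be followed up according to the" DILI checklist.

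**Protocol Table 4.2.1.2:1** (Section 4.2.1.2) repeats the same five signs under its own footnote. It has two rows:
- The row headed "At Visit 2 for new patients (start of treatment") calls for a permanent stop when signs are present.
- The row for any other visit of new patients and "At all visits for roll-over patients" says "Interrupt trial medication (may subsequently need to be permanently discontinued"), followed by a clinical evaluation. Footnote 5 sets three conditions for making the stop permanent: discussion with the sponsor, a confirmed diagnosis and a judgement of relatedness.

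**Cross-references.** The DILI entry in Table 1.4.2:1 sends the reader to Section 4.2.1.2 for liver management. Section 5.2.3 sends the investigator to Section 3.3.4 "for withdrawal criteria" when liver values rise.

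**SAP Section 5.4.3** analyses time to first treatment interruption and "Time to premature treatment discontinuation [days"] as separate items. SAP Section 7.8.1 tabulates AEs leading to permanent treatment discontinuation.

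**The concern.** Both passages start from the same signs but set different conditions for a permanent stop. Section 3.3.4.1 needs attribution alone. Footnote 5 needs relatedness, a confirmed diagnosis and a sponsor discussion. An investigator who follows one cross-reference can reach a different decision from one who follows the other.

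The protocol describes DILI as rare but severe and possibly fatal, and lists hepatic injury as an adverse event of special interest. It should not be left open whether a child may be restarted. For the analysis, the same clinical course could be recorded as a discontinuation at one site and as an interruption at another, so the tolerability outputs would partly reflect which passage a site read.

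**Working it through.** The plan gives no figure to reproduce on this point. The check sets the two rules side by side and runs each possible case through both. The comparison uses the row of the table that covers all visits except Visit 2 of new patients, and case 4 covers that exception.

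| Case | Section 3.3.4.1 | Table 4.2.1.2:1 with footnote 5 | Conflict on the permanent stop? |
|---|---|---|---|
| 1. Signs present, judged not related | This entry does not apply | Interrupt and evaluate; the relatedness condition is not met | No |
| 2. Signs present, judged related, diagnosis confirmed | Permanent stop | Permanent stop after sponsor discussion | No; only the sponsor step differs |
| 3. Signs present, judged related, diagnosis unconfirmed or pending | Permanent stop | Interruption; permanent stop not yet triggered | **Yes** |
| 4. New patient at Visit 2 with signs | Permanent stop if attributable | Permanent stop | No |

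**Does case 3 matter in practice?** It does if interruption leaves a way back to treatment. Table 4.2.1:1 in Section 4.2.1 allows up to 4 weeks of interruption for drug-related events and recommends restarting at the reduced dose. Section 3.3.4.1 closes that route.

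**Is there an order of precedence?** Section 5.2.3 places the withdrawal criteria in Section 3.3.4. Table 1.4.2:1 places liver management in Section 4.2.1.2. No section says which governs when they differ.

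**Effect on the analysis of one case 3 patient** (SAP Sections 5.4.3, 7.8, 7.8.1 and 7.8.1.2):
- *Stopped permanently.* The patient has an event for premature discontinuation and appears in the table of AEs leading to permanent discontinuation. With no earlier interruption, the patient is censored at last intake for time to first interruption. The on-treatment window closes 28 days after that last dose.
- *Interrupted and restarted.* The patient has an interruption event if none came before, and no discontinuation event at that point. The last-intake date moves later, and with it the end of the 28-day window and, for AEs not yet experienced, the end of time at risk.

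**Size per patient.** With approximately 50 to 60 patients planned, one reclassified patient moves an overall proportion by 1/60 = 1.7 to 1/50 = 2.0 percentage points. The documents give no rate of hepatic injury alerts in this population and no share that would fall in case 3, so no expected number can be calculated.

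**The case against.** The strongest reply is that the two passages work in sequence. The signs are an alert. The table gives the immediate step, which is to interrupt and evaluate, and Section 3.3.4.1 gives the outcome once attribution is settled. While evaluation is open, the drug is off under both. Section 3.3.4.1 is mandatory in tone, the table is titled as recommendations, and Section 5.2.3 points to Section 3.3.4 for withdrawal.

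Part of this stands. It narrows the gap and gives a hint about where withdrawal criteria belong. It does not close the gap. Section 5.2.7.1.6 bases causality on medical judgement about a reasonable possibility, which is a lower bar than a confirmed diagnosis, and footnote 5 asks for both. If Section 3.3.4.1 simply prevailed, the confirmed-diagnosis condition would do nothing for attributable signs. Hepatic injury is also reported to the sponsor within 24 hours and the SMC reviews safety data. These are safeguards, but they do not tell the investigator which rule applies.

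Two stronger readings are tempting and are not supported:
- *Every on-treatment alert is affected.* Cases 1, 2 and 4 show that it is not.
- *The table is inverted*, because its milder columns have a recheck rule and the hepatic-injury column has none. The table's column layout was lost in text extraction, so absence is hard to establish. The hepatic-injury column does call for clinical evaluation, the DILI checklist is not available here, and Table 4.2.1:1 already gives interruption limits and a restart dose level. Individual work-up in place of a fixed recheck may also be a deliberate choice.

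**Conclusion.** The contradiction is real but confined to signs judged drug-related while the diagnosis is unconfirmed or pending, at any visit other than Visit 2 of a new patient. There, one passage requires a permanent stop and the other leaves a restart possible.

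The conclusion assumes that footnote 5 states the full condition for a permanent stop in its column, since no other route is given there. It also assumes that the unseen DILI checklist does not settle precedence.

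The statistical effect is on descriptive outputs: AEs leading to permanent discontinuation and time to premature discontinuation, with knock-on effects on time to first interruption and the on-treatment window. The primary endpoint, patients with any treatment-emergent AE, should hardly move. The main reason to act is patient safety. The passages must be reconciled; no view is taken on which clinical rule is right.

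**What to change.** Amend Section 3.3.4.1 and the hepatic-injury column of Table 4.2.1.2:1 with footnote 5, so that one trigger (signs or confirmed diagnosis) and one causality condition govern permanent discontinuation. State in both places whether sponsor discussion is a precondition. Align the cross-references in Table 1.4.2:1 and Section 5.2.3 so that both lead to the reconciled rule. The sponsor and the SMC choose the rule.

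The cost is one wording amendment and a letter to sites, with no new procedures, visits or patients. The SAP needs no change to its definitions.

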3.3.4.2 Withdrawal of consent to trial participation

Patient/parent(s)/legal guardian may withdraw their consent/assent to trial participation, at any time without the need to justify the decision.

If patient/parent(s)/legal guardian want(s) to withdraw consent/assent, the investigator should be involved in the discussion with the patient/parent(s)/legal guardian and explain the difference between trial treatment discontinuation and withdrawal of consent to trial participation, as well as explain the options for continued follow-up after trial treatment discontinuation, please see [Section 3.3.4.1](#) above.

3.3.4.3 Discontinuation of the trial by the sponsor

Boehringer Ingelheim reserves the right to discontinue the trial overall or at a particular trial site at any time for the following reasons:

1. Failure to meet expected enrolment goals overall or at a particular trial site.
2. 
3. Deviations from GCP, the trial protocol, or the contract impairing the appropriate conduct of the trial.
4. 

Further treatment and follow up of patients affected will occur as described in [Section 3.3.4.1](#).

The investigator / the trial site will be reimbursed for reasonable expenses incurred in case of trial termination (except in case of the third reason).

4. TREATMENTS

4.1 INVESTIGATIONAL TREATMENTS

The investigational medicinal products are nintedanib soft capsules 150 mg, 100 mg, and 25 mg. All patients will be treated with nintedanib in this trial; there is no active comparator or placebo.

Nintedanib soft capsules 100 mg (oblong shape, 6.2 mm diameter and 16.3 mm length) and 150 mg (oblong shape, 7.1 mm diameter and 17.6 mm length) are commercially available for adults. Nintedanib soft capsules 25 mg of smaller size (oval shape, 5.1 mm diameter and 8.0 mm length) have been developed for paediatric population. The 75 mg and 50 mg doses will be provided as multiples of the 25 mg dosage strength.

The sizes of the commercially available 100 mg and 150 mg capsules are considered suitable for the targeted age-range. However, for patients who are unable to swallow the commercially available form, a multiple of the 25 mg capsule is proposed as an alternative administration strategy for the 100 mg or 150 mg:

- 4 x 25 mg for the 100 mg
- 6 x 25 mg for the 150 mg

The investigational products will be provided by BI or a designated clinical research organisation (CRO). They will be packaged and labelled in accordance with the principles of Good Manufacturing Practice (GMP).

4.1.1 Identity of the Investigational Medicinal Products

Table 4.1.1:1 Test product 1

Substance:	Nintedanib (Ofev [®])
Pharmaceutical formulation:	Soft gelatin capsule
Source:	Boehringer Ingelheim Pharma GmbH & Co. KG
Unit strength:	150 mg, 100 mg, 25 mg
Posology:	150 mg, or 100 mg, or 3x25 mg, or 2x25 mg, or 25 mg, each b.i.d.
Method and route of administration:	Oral (swallowed)

4.1.2 Selection of doses in the trial and dose modifications

In order to match the systemic exposure reached in adult IPF patients, the nintedanib doses in paediatric patients were predicted based on body weight dependent allometric scaling (scaling of adult clearance using an exponent of 0.75, consistent with the exponent estimated in population pharmacokinetics [PopPK] analyses in adults; refer to the current version of the Investigator's Brochure Nintedanib in Idiopathic Pulmonary Fibrosis, Systemic Sclerosis and Progressive Fibrosing Interstitial Lung Disease [[c01783972](#)] for details).

This approach was considered acceptable, assuming a minor role of developmental changes referring to nintedanib PK for the selected target population. A population mean nintedanib exposure of 80% to 125% compared to adult IPF patients treated with 150 mg b.i.d. was targeted for the determination of the planned doses by body weight bin in the paediatric population.

Confirmation or, if needed, adaptation of the dosing algorithm to achieve nintedanib exposure in pediatric patients comparable to the plasma exposure in adult IPF/SSc-ILD/ chronic fibrosing ILD of a progressive phenotype patients receiving the approved dose of nintedanib 150mg b.i.d. was a part of benefit/risk assessment to be performed in the Phase III parent study InPedILD[®] following DBL1.

Upon confirmation of the algorithm used in the 1199-0337 InPedILD[®] study, the doses of nintedanib will be assigned by body weight bin as shown in table below.

Table 4.1.2:1 Dose assignment and dose reduction possibilities based on body weight bins according to ICH E11

Body weight bin – Provenance of patient	Weight range**	InPedILD [®]	1199-0378	
		Last dose used (b.i.d.) and treatment groups	Dose (b.i.d.) and treatment groups	Dose reduction possibility (b.i.d.)
1 - Patients from Part B of InPedILD [®]	13.5* to <23.0 kg	50 mg or 25 mg*** (nintedanib)	50 mg or 25 mg (nintedanib)	25 mg (nintedanib)
1 - Patients from Part A of InPedILD [®]	13.5 to <23.0 kg	50 mg or 25 mg*** (nintedanib/placebo)	50 mg or 25 mg (nintedanib)	25 mg (nintedanib)
1 - New patients	13.5 to <23.0 kg		50 mg (nintedanib)	25 mg (nintedanib)
2 - Patients from Part B of InPedILD [®]	23.0 to <33.5 kg	75 mg or 50 mg*** (nintedanib)	75 mg or 50 mg (nintedanib)	50 mg (nintedanib)
2 - Patients from Part A of InPedILD [®]	23.0 to <33.5 kg	75 mg or 50 mg*** (nintedanib/placebo)	75 mg or 50 mg (nintedanib)	50 mg (nintedanib)
2 - New patients	23.0 to <33.5 kg		75 mg (nintedanib)	50 mg (nintedanib)

Body weight bin – Provenance of patient	Weight range**	InPedILD®	1199-0378	
		Last dose used (b.i.d.) and treatment groups	Dose (b.i.d.) and treatment groups	Dose reduction possibility (b.i.d.)
3 - Patients from Part B of InPedILD®	33.5 to <57.5 kg	100 mg or 75 mg** (nintedanib)	100 mg or 75 mg (nintedanib)	75 mg (nintedanib)
3 – Patients from Part A of InPedILD®	33.5 to <57.5 kg	100 mg or 75 mg** (nintedanib/placebo)	100 mg or 75 mg (nintedanib)	75 mg (nintedanib)
3 - New patients	33.5 to <57.5 kg		100 mg (nintedanib)	75 mg (nintedanib)
4 - Patients from Part B of InPedILD®	≥57.5 kg	150 mg or 100 mg** (nintedanib)	150 mg or 100 mg (nintedanib)	100 mg (nintedanib)
4 - Patients from Part A of InPedILD®	≥57.5 kg	150 mg or 100 mg** (nintedanib/placebo)	150 mg or 100 mg (nintedanib)	100 mg (nintedanib)
4 - New patients	≥57.5 kg		150 mg (nintedanib)	100 mg (nintedanib)

*patients < 13.5 kg of weight are excluded from the trial.

**Confirmation or, if needed, adaptation of the weight range in the algorithm will be part of benefit/risk assessment in InPedILD®.

***If dose already reduced in InPedILD® or if dose reduction is needed at visit 2. In these cases, no further reduction will be possible. However, for treatment interruption please refer to [Section 4.2.1](#).

New patients:

The patient's weight will be measured at screening and at each IMP dispensing visit (see [Flow Chart](#) for details). The dose assigned will be based on the patient's weight at baseline (Visit 2). At subsequent visits the dose will be adjusted for any changes of the patient's weight resulting in a change of the body weigh bin. IRT will assign the proper dose based on the patient's weight recorded at the respective visit.

Roll-over patients:

Patient will receive nintedanib at corresponding dose assigned in the parent trial, whether the patient was previously assigned to the nintedanib or the placebo treatment group. If the patient's weight has changed such that a different dose is required (please refer to [Table 4.1.2: 1](#)), the appropriate dose of nintedanib will be assigned.

For those patients who dose reduced in the parent trial, the dose can stay reduced or be increased based on the judgement of the investigator.

Similar to the parent trial, treatment interruption and dose reduction to the next lower dose are allowed to manage adverse events.

